604 proportion of bile leaks, for example, of 0.18 in the cadaveric group versus 0.30 in the
605 LDLT group (a difference of 0.12). Physician estimates of this difference are closer to
606 0.20, so power is more than sufficient for this endpoint. If we more conservatively
607 assume complication proportions near 0.5, we will have 89% power to detect a difference
608 of 0.14 (such as 0.43 versus 0.57).

609 **4.6.5. Statistical Analysis**

610 Analysis of LDLT donor post-operative complications will be descriptive. We will
611 report the proportions of donors with complications such as bile leak, primary non-
612 function, graft failure, pneumonia, and urinary tract infection, as well as any complication
613 requiring hospital admission, re-operation, or other intervention. Confidence intervals
614 will be included with all estimates. We will also report follow-up outcomes including
615 wound healing, pain medications, blood laboratory values, and the proportion of patients
616 who returned to work/school. Some attempt will be made to correlate complications with
617 patient characteristics and operative procedures, but any such analyses will be limited by
618 the quality of available data.

619
620 LDLT recipient post-operative complications will be reported in the same way as the
621 donor complications described above. In addition, a comparison of LDLT complications
622 with complications following cadaveric transplant will be made. Depending on the type
623 of complication (event occurrence, time to event, or continuous outcome), a comparison
624 of the events between LDLT and cadaveric transplants will be made using logistic
625 regression, Cox regression, or ordinary regression, respectively, each adjusted for other
626 predictive variables as needed.

627 **4.7. Retrospective Resource Utilization Study**

628 **4.7.1. Study Methods**

629 Length of hospitalization, days in ICU, and major interventions will be used as measures
630 of resource utilization. Note: Incorporation of cost and charge data is not planned. Such
631 information is both difficult to obtain and to interpret.

632 **4.7.2. Participant Selection**

633 The cohort will include all of the following:

634 Potential recipient listed for transplantation

- 635 • age \geq 18
- 636 • single organ

637

638 Potential donor evaluated between 1/1/1998 and the start date of enrollment into the
639 A2ALL-Cohort-01 Study.

640 **4.7.3. Data Elements**

641 Hospitalization admission and discharge dates (pre-transplant and post-transplant).

642 Number of ICU days. Major interventions performed during inpatient hospitalizations

643 **4.7.4. Sample Size and Power Calculations**

644 For comparing hospitalization between LDLT recipients and non-recipients we consider
645 the number of hospital days in one year. Although the analysis will take into account the
646 possibility that some patients may be included in both groups, both pre- and post-LDLT,
647 the power calculations consider a similar but simplified design based on a two-sample t-
648 test (2-sided, $\alpha=0.05$), assuming 300 LDLT recipients and 500 non-recipients. We
649 have no preliminary data on means or standard deviations (s.d.s) for number of hospital
650 days in a year, but assuming a fairly large s.d. of 25 days, we will have 93% power to
651 detect a difference of 5 days (effect size = 0.20 s.d.) between LDLT and non-LDLT
652 groups.

653 **4.7.5. Statistical Analysis**

654 Resource utilization, particularly hospitalization (number of hospitalizations and number
655 of hospital days) will be compared for those with and without LDLT using a repeated
656 measures logistic regression analysis. In addition, a comparison of hospitalization after
657 LDLT versus cadaveric transplant will be made.

658 **5. Human Subjects**

659 **5.1. Protection of Human Subjects**

660 **5.1.1. Institutional Review Board**

661 This data collection and analysis will be performed under Institutional Review Board
662 (IRB) oversight. Prior to the initiation of the study, an IRB approval for study of human
663 subjects will be obtained separately from the IRB of each of the participating transplant

664 centers and the DCC. Revisions to the study protocol and changes in the study design
665 will also be submitted to IRBs for approval prior to implementation.

666

667 Each center will complete an application to their own IRB to allow receipt of the center-
668 specific SRTR-identified data set and the abstraction of additional information from the
669 medical record and release of this identified information to the DCC for analysis. The
670 application will request a waiver of written informed consent for this retrospective
671 project. The DCC will also have in place an IRB approved protocol to complete its
672 responsibilities for the study. The DCC will, in turn, receive identifiable data from the
673 centers to allow for linking to the prospective study in the future to avoid the need for
674 duplicative data collections.

675

676 In order to plan a successful prospective study it is important to include all adult-to-adult
677 donors and recipients of living donor liver transplants. Because the numbers are large
678 and span a five-year period it would be extremely difficult to obtain written informed
679 consent for all subjects in the data set. Therefore, each transplant center will request a
680 waiver of informed consent for this data collection and release of patient identified
681 information. The following paragraphs delineate the rationale for requesting a waiver of
682 informed consent for the retrospective study.

683

684 Waiver of project-specific written informed consent is possible if a project meets the
685 following four criteria derived from Section 45 CFR 46.116 (d). "An IRB may ... waive
686 the requirements to obtain informed consent, provided the IRB finds and documents
687 that:"

688

689 1. The research involves no more than minimal risk to the research subjects. 45 CFR
690 46.102 (I) defines minimal risk as: the probability and magnitude of harm or
691 discomfort anticipated in the research are not greater in and of themselves than those
692 ordinarily encountered in daily life of during the performance of routine physical or
693 psychological examinations or tests.

694

695 2. The waiver or alteration will not adversely affect the rights and welfare of the
696 research subjects.

697

698 3. The research could not be practicably be carried out without the waiver or alteration;
699 and;

700

701 4. Whenever appropriate, the subjects will be provided with additional pertinent
702 information after participation.

703

704 The proposed A2ALL retrospective study meets the above four criteria necessary for
705 consideration of a waiver of consent.

706

707 1. The research will abstract information that was collected in standard medical records
708 during routine medical evaluation and follow-up. The risk to the subject of this data
709 abstraction is judged to be minimal. Safeguards are in place to keep the information

- 710 confidential utilizing a secure server for web-based data entry. The data will be
711 stored on a secure server within the University of Michigan computer system.
712
- 713 2. A waiver of written informed consent will not adversely affect the rights or welfare of
714 the research subjects. These data will consist of routine laboratory and procedure
715 results, complications and outcomes of surgery and overall level of health that have
716 been recorded in the subject's medical record. It is important to keep this data linked
717 to the subject to avoid the need to "recollect" the data for use in the planned
718 prospective clinical trial.
719
- 720 3. The inclusion of every living donor liver recipient and donor from each of the
721 A2ALL transplant centers is necessary for the planning the prospective study. There
722 are well-documented investigations of the bias introduced by the informed consent
723 process. In order to avoid this bias and examine the overall effect of this procedure,
724 every patient that has participated in this procedure must be examined. Successfully
725 locating, contacting and securing informed consent from each subject is
726 "impracticable". The results of this retrospective analysis will guide the
727 development of a 5-year prospective longitudinal investigation of this study
728 population. All eligible retrospective study subjects will be approached and informed
729 consent will be documented for the prospective study. Only the retrospective study
730 subjects that are able to be contacted and provide written informed consent will be
731 enrolled into the prospective study.
732
- 733 4. Information that is revealed from this study will be presented at transplant meetings
734 and published in scientific periodicals. The NIH will also utilize press releases to
735 communicate the study findings. In this manner, information that may affect the
736 previous subjects will be communicated.
737

738 Additionally, this study meets the requirements for a waiver of consent under the new
739 HIPAA guidelines.

740 The HIPAA requirements for a waiver of consent (164.512(i)(2)(ii)) are:

- 741
- 742
- 743 1. No more than minimal risk to subject (*addressed above*)
744
- 745 2. Plan to protect identifiers from improper use/disclosure
746
- 747 *Secure web servers and limited access to the data will protect the data from improper*
748 *use/disclosure*
749
- 750 3. Plan to destroy identifiers at earliest opportunity consistent with conduct of research
751 unless retention required by law or research design
752

753 *The links will be removed as soon as determination of ability to contact subject for*
754 *prospective study has been made. Any subject contacted and not interested in*
755 *participating, any subject that is deceased and any subject that can not be located*

756 *will have identifiers destroyed. The remainder will have the links maintained after*
757 *consent is obtained and they will be enrolled into the prospective study. Data sets for*
758 *this retrospective study will be coded and have identifiable information removed*
759 *prior to analysis by the DCC.*

760

761 4. Written assurances that Private Health Information (PHI) will not be reused or
762 disclosed except as required by law or oversight

763

764 *The DCC will provide a written assurance that the information will be not reused or*
765 *disclosed.*

766

767 5. Can't do research without waiver

768

769 *Significant bias introduced without waiver is addressed above.*

770 6. Can't do research without access to and use of PHI.

771

772 *The need to link to potential prospective data in the next study is discussed above.*

773 *The DCC will be requesting data sets from the SRTR that contain identifiable*

774 *information and will distribute these to the individual transplant centers that*

775 *originally submitted the data. The DCC will receive the data set back from the*

776 *transplant centers with corrections and additions of the original data as well as*

777 *additional data elements obtained from medical record review. The DCC will*

778 *maintain these links until the prospective study begins and will destroy the links for*

779 *non-participants in the prospective study. At all times the data will be stored and*

780 *transferred via secure data servers that require username and password access.*

781 **5.1.2. Patient confidentiality**

782 Special procedures for ensuring patient confidentiality will be implemented. Data
783 transmission and the distributed data systems have multiple layers of security as
784 discussed in the study management section. Each study subject will be assigned an
785 identification number. Only this number will be used to identify subjects in any
786 individual tabulation. It is expected that only group data will be published. If individual
787 subject data are to be published, no identifying information will be included. The study
788 files will be maintained in a secure location as described above. Access to computerized
789 data will be restricted to study personnel. Password authorization will be enforced. These
790 passwords will be changed on a quarterly basis and whenever the Database Administrator
791 makes a determination for a security change. Previous use of this security system and
792 secured server indicates that this technique is very successful in assuring the protection of
793 confidential information.

794

795 Authorized representatives of the Sponsor, the National Institute of Diabetes, Digestive
796 and Kidney Diseases (NIDDK), National Institute of Health (NIH), participating clinical
797 institution, DCC monitoring staff, as well as the IRB, have access to medical records and
798 records from participation in this study. Such access is necessary to ensure the accuracy
799 of the findings.

800 **5.1.3. Risks to the patient**

801 This data collection represents no more than minimal risk to the subjects and does not
802 contain sensitive information. All data scheduled for collection and analysis have already
803 been collected and documented as a part of standard clinical care. It would be
804 impracticable to find, contact and obtain informed consent from each subject in the study
805 group. This study meets the federal guidelines for a waiver of informed consent.

806 **5.1.4. Unauthorized data release**

807 The data sets will be stored on a secure server with restricted access (requires a unique
808 username and password) at the DCC and every precaution will be taken to keep the
809 information private. However, there is always the possibility of unauthorized release of
810 data about subjects. Such disclosure would be extremely unlikely to involve a threat to
811 life, health, or safety but would be a serious invasion of the subject's privacy. It is
812 conceivable that such disclosure could have psychological, social, or legal effects on the
813 patient. Using the standard security procedures (described above under patient
814 confidentiality) can effectively minimize the risk of unauthorized disclosure of data. All
815 study personnel who have access to patient data will be educated regarding the need to
816 protect confidentiality and the procedures to be followed to ensure such protection. All
817 staff will also be required to sign a standard medical record confidentiality agreement.
818 The computer system on which data are maintained uses standard password protection
819 procedures to limit access to authorized users. It is envisaged that the DCC will provide a
820 second level of security checks. Data to be used for analysis will contain only the
821 assigned identification numbers. All patient identifiers such as name, address and hospital
822 record identification number will not be accessible to the staff involved in carrying out
823 data analysis.

824 **5.2. Benefits to the Patients**

825 There are no direct benefits to the patients for participation in the study.

826 **5.3. Inclusion of Women**

827 This is a multi-center study drawing on a clinical population from nine transplant
828 institutions across the United States. The demographics of the study population are pre-
829 determined due to the retrospective all-inclusive nature of the study. Women will be
830 included in the retrospective study as living liver donors and recipients. It is anticipated
831 that the representation of women will correspond to the fraction of females in the living
832 liver donor and recipient population.

833 **5.4. Inclusion of Minorities**

834 This is a multi-center study drawing on a clinical population from nine transplant
835 institutions across the United States. The demographics of the study population are pre-
836 determined due to the retrospective all-inclusive nature of the study. Racial and ethnic
837 minority groups will be included in the donor and recipient components of the
838 retrospective study and will be proportional to their representation in the donor and
839 recipient population.

840 **5.5. Inclusion of Children**

841 The Adult-to-adult living donor liver transplantation cohort study specifically excludes
842 children.

843 **5.6. Data and Safety Monitoring Plan**

844 Accepted principles of data and safety monitoring will be observed throughout the
845 conduct of the A2ALL retrospective study. Since the retrospective study is restricted to
846 review of information in the medical record, no adverse events will occur or be reported.

847
848 Each transplant center principal investigator will be responsible for monitoring the
849 A2ALL retrospective study, as will the DCC. Monitoring responsibility will extend to
850 determination of accurate and effective conduct of the protocol and to recommendations
851 regarding closure of the study.

852
853 Oversight of monitoring will be performed to ensure that: 1) monitoring activities are
854 appropriate to the study, 2) monitoring is accomplished in a regular, timely and effective
855 way and 3) recommendations that result from study monitoring are completed.

856
857 IRBs will be provided feedback on a regular basis.

858

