37 outcomes will be compared with those of transplant candidates who are evaluated for but
38 do not receive LDLT. The primary objective concerns comparison of morbidity and
39 mortality of patients who receive LDLT with a group or groups of patients with similar
40 illnesses and prognoses. It is also important to compare the outcomes after LDLT to
41 those after cadaveric transplantation. Transplant physicians need this information on
42 outcomes to advise patients and prospective donors. Therefore, sufficient patient and
43 donor pairs will be recruited to determine whether recipients of LDLT have substantially
44 different survival than non-LDLT recipients. A large number of donors and recipients

45 from several geographically distributed institutions will be necessary to reliably
46 determine if outcomes are different with the two approaches.

47
48 These issues are best addressed through prospective data collection. But, the main
49 outcomes of the A2ALL prospective data collection will not be available for at least 5
50 years. Therefore, to gain initial insights into outcomes associated with these procedures,
51 a retrospective cohort or look back study has been designed to compare the outcomes of
52 LDLT and cadaveric liver transplants and the outcomes for living liver donors beginning
53 in 1998 at the nine participating transplant centers of the A2ALL study. In order to be
54 conducted rapidly and efficiently, this study will rely exclusively on existing medical
55 records and patient materials.

56 **3. Study Objectives/Specific Aims**

57 **3.1. Overall Aim of the Retrospective Cohort Study**

58 The primary study objective is to determine whether the *decision* to undergo LDLT is
59 beneficial for the patients who choose LDLT. The principal hypothesis is that receipt of
60 a living liver allograft leads to better long term outcomes for liver transplant candidates
61 than *pursuit* of cadaveric transplant. This is a study of the decision to perform LDLT.
62 Several different patient outcomes will be considered.

63 **3.2. Comparison of mortality between LDLT and non-LDLT recipients**

64 **3.2.1. Primary Aim**

65 To compare the survival distribution from time of identification of a potential living
66 donor between those receiving an LDLT and those not receiving one.

67 **3.2.2. Secondary Aims**

68 To compare the survival of LDLT vs. cadaveric recipients from time of transplant.

- 69

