110 To ascertain which data elements collected via the OPTN data collection process can be
111 reliably employed for use in the prospective A2ALL Cohort Study.

112
113 To provide feedback to the SRTR and OPTN on the accuracy and completeness of
114 selected data elements.

115 **3.6. Retrospective Post-surgical Complications Study**

116 **3.6.1. Primary Aim**

117 To determine the rate of the major donor post-operative complications associated with
118 planned right lobe liver donation

119

120 To compare the major recipient post-operative complications after LDLT versus
121 cadaveric transplant.

122 **3.7. Retrospective Resource Utilization Study**

123 **3.7.1. Primary Aim**

124 To compare the resource utilization for patients who proceed to LDLT versus those for
125 whom living donation does not occur and thus proceed toward cadaveric transplant.

126 **4. Investigational Plan**

127 **4.1. Overall Study Design**

128 Most of the specific aims require LDLT recipients and control patients who did not
129 undergo LDLT. However, the identification of these controls and study start time (time
130 0) for following LDLT patients and controls will differ for the various objectives. All, or
131 nearly all, of the LDLT recipients will be included in all analyses, which will simplify
132 chart review. Many of the control patients will also be included in several analyses.
133 LDLT donors will be evaluated for surgical complications.

134

135 For the primary survival and resource utilization objectives, the study entry point is at
136 initial evaluation of a potential living donor that includes history and physical
137 examination at the transplant center. The overall design of the retrospective cohort study
138 is predicated on this definition as the starting point for inclusion in the cohort. In the
139 primary analysis (see below), the mortality of LDLT patients will be compared to
140 mortality of patients who have not yet had LDLT, regardless of subsequent events
141 (cadaveric transplant, death, or removal from waitlist for any other reason). This cohort
142 will include all those evaluated for LDLT transplants from 1/1/98 until 2/28/03. Among
143 the 9 transplant centers in the A2ALL project, approximately 40% of individuals who had
144 a potential living donor identified went on to undergo LDLT, leaving 60% as controls
145 (see Feasibility Study report [Appendix A]). Based on this report, we estimate that

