178 For certain endpoints, supplementation of cadaveric controls above those identified in the
179 retrospective cohort component of the study may be necessary. Augmentation with
180 contemporaneous cadaveric controls would most likely occur for the first one to two
181 years of a program's experience. If additional patients are required, they will be
182 identified using SRTR data, frequency matching to the characteristics of recipients
183 undergoing LDLT. Potentially, a few LDLT patients could be included in this group but
184 excluded from the primary objective analysis. This situation would arise if a donor
185 evaluation occurred in 1997, resulting in LDLT in early 1998, although this comprises a
186 very small number of patients. We anticipate supplementation with no more than 100 to
187 200 transplant recipients.

188

189 The final cohort will include the LDLT donors (approximately 300).

190 **4.2. Comparison of mortality between LDLT and non-LDLT recipients**

191 **4.2.1. Study Methods**

192 The primary aim will use the cohort of subjects evaluated for LDLT. Survival from time
193 of donor evaluation will be compared among those receiving and not receiving LDLT. In
194 addition, we will compare both survival and rejection episodes for LDLT vs. cadaveric
195 recipients from time of transplant.

196

197 Primary endpoint: Time of death or last known alive.

198 Secondary endpoint: Time from transplant to rejection episode, or last known time
199 without rejection, incidence, number and severity of rejection and incidence of steroid-
200 resistant rejection during the 1st post-transplant year.

201 **4.2.2. Participant Selection**

202 The cohort will include all of the following:

203 Potential recipient listed for liver transplantation

- 204 • age \geq 18
- 205 • single organ

206

207 Potential donor evaluated with history and physical examination occurring between
208 1/1/1998 and the start date of the A2ALL-Cohort-01 Study enrollment. This date will be
209 different for each clinical site and will be determined once site initiation is completed and
210 the site is ready to begin enrollment of prospective subjects.

211 **4.2.3. Data Elements**

212 Two limitations of chart reviews must be kept in mind: Information may be missing, and
213 information may be inaccurate. Because these problems can occur systematically, results
214 can be biased. A2ALL will be circumspect about collecting information that is limited in

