215 either respect. Sample records will be examined for completeness and ease of obtaining
216 information on all data elements before formal data collection begins.

217

218 a. At listing

219 Date of listing

220 DOB, sex, ethnicity (PHS categories)

221 Reasons for transplantation (list primary and secondary diseases)

222 MELD/UNOS status/CTP score at time of listing

223

224 b. Potential Donor

225 Date of each donor evaluation

226 Information on potential donor. Data collection on donors will largely be limited to
227 clinically significant pre- and post-donation events and a small amount of operative
228 information.

229 Donor outcome information

230 Reasons for not donating for those who do not donate

- 231 - Medical or psychological for donor
 - 232 o Medical condition (liver related vs. co-morbid medical conditions)
 - 233 o Anatomical
 - 234 o Size
 - 235 o Blood type
 - 236 o Psychological
- 237 - Donor declines/changes mind
- 238 - Recipient became too sick (or too well)
- 239 - Recipient received cadaveric transplant
- 240 - Other

241 Date of decision not to donate

- 242
243 c. Pre-transplant
244 Complications (treated ascites, treated SBP, variceal bleed, other GI bleeds requiring
245 transfusion, hepatorenal, hepatopulmonary, treated encephalopathy, TIPS,
246 portopulmonary hypertension, bony fracture [yes or no for each])
247 SBP Prophylaxis (yes/no)
248 Antiviral therapy (specific to HBV and HCV)
249 Changes in MELD, CTP, OPTN/UNOS status
250 Hospitalization admission and discharge date
251 Days in ICU
252 Death
253 Dates for each of these
254
255 d. Transplantation and beyond
256 Date of transplant
257 Selected intra-operative data
258 Hospitalization dates
259 Days in ICU
260 Retransplantation
261 Baseline immunosuppression regimen (tacrolimus, cyclosporine, or non-calcineurin
262 antagonist based); antibody induction (yes/no)
263 Treated rejection episodes within one year of transplant:
264 1. Date of rejection (treated rejection episodes separated by less than 22 days will be
265 considered the same event for analysis purposes).
266 2. Liver biopsy (when performed): Acute rejection severity as recorded in the
267 original pathology reading (mild, moderate, severe or undetermined)
268 3. Immunosuppression at transplant and at the initiation of anti-rejection therapy
269 4. Drugs used to treat rejection

270 **4.2.4. Sample Size and Power Calculations**

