1057 instructions on the use of BioDBx, data element definitions and a code list will be
1058 provided in a Manual Of Operations (MOO). Each study site will be provided a copy of
1059 the MOO and the entire manual will be available on the study web site.

1060 **9. Expected Publications**

- 1061 A. Mortality and major morbidity consequent to choosing LDLT (primary objective)
- 1062 B. Recurrence of and other outcomes of hepatitis C post-LDLT
- 1063 C. Descriptive experience of post-LT HCC outcomes according to pre-LDLT variables.
- 1064 D. Donor complications
- 1065 E. Post-LDLT recipient outcomes (requires prospective identification of the outcomes
1066 that would be reported).
- 1067 F. Validation of SRTR (a longer report could be provided to HRSA, OPTN)

1068 **APPENDICES**

1069 **Appendix A. Feasibility Study**

1070

Summary Year	Total	Received LDLT		Received CAD		Died/Removed from List		Still Waiting	
	LDLT Candidates	Number	%	Number	%	Number	%	Number	%
1998	35	27	77%	4	11%	4	11%	0	0%
1999	99	54	55%	26	26%	16	16%	3	3%
2000	155	61	39%	37	24%	28	18%	29	19%
2001	275	99	36%	53	19%	40	15%	83	30%
2002	298	94	32%	61	20%	19	6%	124	42%
Total	862	335	39%	181	21%	107	12%	239	28%

Northwestern Year	Total	Received LDLT		Received CAD		Died/Removed from List		Still Waiting	
	LDLT Candidates	Number	%	Number	%	Number	%	Number	%
1998	0	0		0		0		0	
1999	5	2	40%	2	40%	1	20%	0	0%
2000	17	7	41%	4	24%	2	12%	4	24%
2001	13	9	69%	1	8%	2	15%	1	8%
2002	23	10	44%	6	26%	3	13%	4	17%
Total	58	28	48%	13	23%	8	14%	9	16%

VCU Year	Total	Received LDLT		Received CAD		Died/Removed from List		Still Waiting	
	LDLT Candidates	Number	%	Number	%	Number	%	Number	%
1998	17	12	71%	1	6%	4	24%	0	0%
1999	36	25	69%	5	14%	4	11%	2	6%
2000	16	11	69%	3	19%	1	6%	1	6%
2001	21	7	33%	3	14%	7	33%	4	19%
2002	29	9	31%	4	14%	1	3%	15	52%
Total	119	64	54%	16	13%	17	14%	22	18%

1071

UVA Year	Total	Received LDLT		Received CAD		Died/Removed from List		Still Waiting	
	LDLT Candidates	Number	%	Number	%	Number	%	Number	%
1998	0	0	0%	0	0%	0	0%	0	0%
1999	6	3	50%	3	50%	0	0%	0	0%

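### Primary mortality endpoint: no common closing date and no stated way to find deaths after delisting, so censoring may be informative and may differ between groups

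*Protocol*

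**What the plan says.** - **Endpoint (4.2.1):** "Primary endpoint: Time of death or last known alive". No date is given to which vital status is to be established.
- **Source (Section 2):** "this study will rely exclusively on existing medical" records.
- **Who counts as a control, and for how long (4.1):** LDLT patients are compared with the "mortality of patients who have not yet had LDLT, regardless of subsequent events". The events named are "cadaveric transplant, death, or removal from waitlist for any other reason". Delisting therefore does not end a control's follow-up by design.
- **Data elements (4.2.3):** Death, with its date, stands in list c, the pre-transplant items. The list headed "d. Transplantation and beyond" has no death item and no date of last contact. Neither list names the date and reason of waitlist removal. The nearest items are dated changes in OPTN/UNOS status and a reason for non-donation that puts recipients who became too sick and those who became too well in one category.
- **SRTR (5.1.1):** "The DCC will be requesting data sets from the SRTR that contain identifiable" information. The stated uses are selection of supplementary controls (4.1, 4.3, 4.6.2), validation of selected items (4.5) and a check of representativeness (7.3).
- **Identifiers (5.1.1):** these are destroyed for subjects who have died, cannot be located or decline the prospective study.
- **Feasibility (Appendix A):** deaths and removals are counted together in a column headed "Died/Removed from List".

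**The concern.** Section 4.1 sets a requirement that 4.2.1 and 4.2.3 do not equip the study to meet. A transplant recipient has a continuing reason to appear in the center's records. A control taken off the list may not, and the protocol does not say where that person's later status would be looked up, or up to what date. If follow-up is less complete in one group, and if completeness depends on prognosis, then censoring at last known alive is informative and differs between the groups that the primary aim compares. This would affect both Cox analyses in 4.2.5. The listed covariates would not repair it, because the loss would depend on what happened after entry.

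Timing matters too. A later analysis plan cannot recover a date that was never abstracted, and once links are destroyed for subjects who cannot be located, a further search for their deaths is closed off.

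**Working it through.** **1. The plan's own figure.** Section 4.2.4 gives 300 LDLT recipients, 500 non-recipients, a two-sided logrank test at 0.05, exponential survival and one-year survival of 0.875 with LDLT. It states 82% power for control survival of 0.83 or 0.91, and 93% for 0.82 or 0.92. The length of follow-up is not given, so these figures cannot be reproduced from the stated inputs alone.

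- With one year of follow-up and control survival of 0.83, expected deaths = 300 × 0.125 + 500 × 0.17 = 122.5.
- HR (control/LDLT) = ln 0.83 / ln 0.875 = 0.1863 / 0.1335 = 1.395, and ln HR = 0.333.
- Schoenfeld: 0.333 × √(122.5 × 0.375 × 0.625) − 1.96 = −0.175, so power is 43%. Other standard logrank formulas give 39 to 40%.
- Fixed follow-up of about 3.6 years brings all four stated figures within about 3 points by those other formulas, and within 4.7 points by Schoenfeld.

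I do not count this as an error. It shows only that the power statement relies on several years of follow-up, while the protocol sets no closing date.

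**2. What the passages provide for a control who is delisted and later dies.**

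| Needed | Provided |
|---|---|
| Rule that the death counts | Yes, 4.1 |
| Date to which status is sought | No |
| Source for a death after delisting | Existing records only; SRTR not assigned to this |
| Date and reason of removal | Not a named item; too sick and too well merged |
| Date last known alive | Needed by 4.2.1, not listed in 4.2.3 |

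**3. Sensitivity of the hazard ratio.** Let m be the share of control deaths missed and p the share of control person-time lost through survivors dropping out. Both are assumptions; the protocol gives neither. The observed control rate is the true rate × (1 − m)/(1 − p). Take true control survival as 0.83, hence HR 1.40, and LDLT follow-up as complete.

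| Assumed loss | Apparent one-year control survival | Apparent HR |
|---|---|---|
| None | 0.830 | 1.40 |
| m = 10% | 0.846 | 1.26 |
| m = 20% | 0.862 | 1.12 |
| m = 30% | 0.878 | 0.98 |
| p = 10% | 0.813 | 1.55 |
| p = 20% | 0.792 | 1.74 |
| p = 30% | 0.766 | 1.99 |

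For example, at m = 20%: 0.1863 × 0.8 = 0.1491; exp(−0.1491) = 0.862; 0.1491 / 0.1335 = 1.12. With p = 0 the effect vanishes at m = 1 − 0.1335/0.1863 = 28%. When m equals p the rate is unbiased.

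**4. Can Appendix A size it?** Non-LDLT candidates number 862 − 335 = 527. Of these, 107 (20%) died or were removed. Because the two are pooled, the number delisted alive is unknown. If 10 to 50% of the 107 had been delisted alive and died unseen, that would be about 11 to 54 deaths. Nothing in the documents selects a value in that range.

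**The case against.** The strongest reply is that this is a gap in detail and not a bias. Much of it stands.

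- **The endpoint line is ordinary right-censoring.** It does not censor at delisting, and 4.1 keeps delisted controls in. A reader might infer that controls removed as too sick leave follow-up just before death, so that control mortality is understated and the comparison is biased against LDLT. The documents do not support that: they say nothing about how long delisted patients stay in the records.
- **The direction is open.** Patients who became too well can drop out too, and deaths may be recorded more readily than continued survival. Either would overstate control mortality.
- **The missing death item points the other way.** A never-transplanted control falls under the pre-transplant list, which has Death. Read literally, the omission would lose recipients' deaths. It is probably an oversight, since 4.3.5 plans to censor deaths from other causes after transplant.
- **A tempting magnitude fails.** A reader might compare the one-year difference of 500 × (0.875 − 0.83) = 22.5 deaths with the 107 died or removed. The 107 accumulated over several years. At 3.6 years the same hazards give 500 × (0.875^3.6 − 0.83^3.6) = about 53.5 deaths, so the two counts are not on one scale.
- **The preferred analysis is partly protected.** Its controls must be alive and eligible at the matched time, so those already delisted are not selected. Controls delisted afterwards remain exposed.
- **Some safeguards exist.** Section 4.2.3 warns of systematic chart gaps and checks sample records first. Section 4.2.5 will evaluate whether becoming too sick is rare. SRTR data sets return from the centers with corrections, and Section 8 leaves definitions to the manual.

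These safeguards do not close the gap. None says how, or to what date, vital status is established after delisting. The validation study does not say that death is among its items, and it excludes subjects first evaluated after 2/28/03, whereas the 4.2.2 cohort runs to each site's prospective start.

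**Conclusion.** The point holds as a worthwhile and inexpensive improvement. The protocol requires control mortality to be followed through delisting but fixes no closing date, no source for later deaths, and not all of the dates that its own endpoint needs. Censoring may therefore be informative and may differ between groups.

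Neither direction nor size can be determined. The sensitivity figures rest on assumed loss shares, exponential survival, complete LDLT follow-up and a true HR of 1.40. They show that moderate incompleteness among controls could erase the difference the study is powered for, or enlarge it considerably. They do not show that either will happen, and a demonstrated bias against LDLT should not be claimed.

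**What to change.** - **4.2.1:** set one vital-status cut-off date per site. Establish alive or dead at that date for every cohort member (LDLT, cadaveric, delisted, still waiting) by the same search of the center chart and the SRTR record, completed before any identifiers are destroyed under 5.1.1. Censor at the cut-off. Use last contact only where both sources are silent, and report the number of such patients by group.
- **4.2.3:** add post-transplant death, date last known alive, and date and reason of waitlist removal, with too sick recorded separately from too well.
- **4.2.5:** add a sensitivity analysis that counts patients removed as too sick, with no later status known, as deaths at removal.

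The cost is protocol wording, a few more fields, some linkage work and one extra analysis. No patient contact is needed. A common cut-off with an identical search guards against error in either direction, so the fix does not depend on knowing which way any bias would run.
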